Visit 2: 70 FHD subjects and 70 HV from visit 1 will be recruited to undergo a functional MRI brain at Duke BIAC. To assess patient's baseline, subjects will copy a sentence using their dystonic **left or right hand** in fMRI suite alternated by periods of rest using an MRI compatible digital tablet. Writing task and control motor task will be back-projected onto a screen located at the head of the MRI bed using an LCD projector. Subjects will view the screen via a mirror system located in the head coil. Task onset will be electronically synchronized with the MRI acquisition computer using Cigal computer software. Task administration and collection of writing data will be computer controlled. The scanning session will take about 1.5 hr and include structural MRI, DTI, Swan, resting state fMRI and task-based fMRI.

BOLD images will be acquired using a GE Premier Performance 3T MRI scanner, which is an improved version of GE's FDA-approved Premier system, but with better capabilities for high-resolution imaging. All operational parameters on this improved system will be within FDA guidelines to meet the same minimal risk device criteria and ensure safety of human subjects. As such, an Investigational Device Exemption (IDE) is not necessary. The research conducted under this protocol is not to evaluate the safety and efficacy of this device.

A urine drug screen and pregnancy test prior to visits 3-5.

Visits 3, 4 and 5: 5 healthy volunteers who completed visits 1 and 2 will be recruited to undergo development of TMS stimulation protocol at Duke BSRC. Following protocol development, 20 focal hand dystonia subjects who completed visits 1 and 2 will also be recruited to undergo TMS stimulation at Duke BSRC. All 25 subjects will undergo the procedure as detailed below:

[figure not shown]

Figure 3: Sequence of events for research visits 3, 4, and 5. A) Overview of TMS stimulation, writing assessment and fMRI imaging. B) TMS session will be divided into 4 blocks of writing, each 5 minutes.

1. MRI Brain images from visit 2 will be uploaded to a neuro-navigation system (Brainsight: Rogue Research, Montreal, Canada) at the Brain Stimulation Service Stimulation Service Center

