 3. Healthy volunteers will undergo TMS stimulation protocol development. Subjects will receive 10Hz active stimulation at premotor cortex during one visit and primary sensory cortex during another visit for up to 20 minutes with stimulation intensity up to 120% of resting motor threshold which is within the published safety guidelines (47) and based on previously published protocol used in multiple human studies(13–16). The resting motor threshold is a baseline stimulation intensity determined using the protocol in step 2. Additional stimulation parameters including duration of continuous stimulation, interstimulus interval, stimulation intensity, orientation of magnetic coil, biphasic or monophasic stimulation will be developed with healthy volunteers based on the published safety guidelines(47), writing assessment (includes writing and non-writing sampling) and feasibility within 20 minutes stimulation paradigm.
 4. WC subjects will undergo TMS stimulation visits 3, 4 and 5. 2 visits will include active TMS stimulation while the remaining one visit will be a control sham stimulation. Of the 2 active TMS stimulation visits, subjects will receive TMS at premotor cortex during one visit and at primary sensory cortex during the other active TMS visit. The dosage of active stimulation will be 10Hz for up to 20 minutes with resting motor threshold up to 120% which is within the published safety guidelines (47) and based on previously published protocol used in multiple human studies(13–16). During both active and sham stimulation blocks, subjects will be asked to perform a writing task of writing a diverse paragraph as an online stimulation task. The stimulation block will be preceded and followed by a writing assessment and TMS acute side effects survey to assess safety of the stimulation. Visit 3, 4, and 5 will occur 1 week apart. Subject will undergo fMRI after each of the 3 TMS visits.

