fMRI data: All image pre-processing will be implemented using the FSL program (<https://wiki.biac.duke.edu/biac:fsl>). Block design fMRI data will be extracted by time-series modeling using rectangular time windows for the motor task and rest periods. Group data will then be analyzed using GLM modeling. Any fMRI network identified in writing performance from previous fMRI research using the writing task in dystonia patients will be prospectively applied to the fMRI data of the subjects. Specifically, the imaging data from the pre and post fMRI sessions will be log transformed and subtracted from each other at each site in each subject. The global mean across sites will be subtracted from each log-transformed regional value, producing regional values normalized to each subject's global mean activity. In a second normalization, the mean for each site across subjects will be subtracted from each regional value. The result of these two normalizations is a subject x region matrix with the mean activity within and across subjects removed. This will be cross-correlated with the patterns previously found in order to quantify pattern expression for individual subjects in the present group. These individual subject pattern expressions will be entered into regressions predicting brain performance in order to verify that the patterns predict performance in new group. In addition, pattern expression will be used to predict rTMS effects on writing task performance (for example, differences in RT with active and sham rTMS).

Data & Safety Monitoring

- Summarize safety concerns, and describe the methods to monitor research subjects and their data to ensure their safety, including who will monitor the data, and the frequency of such monitoring. If a data monitoring committee will be used, describe its operation, including stopping rules and frequency of review, and if it is independent of the sponsor (per 45 CFR 46.111(a) (6)).

Safety monitoring: The subjects will be fully informed of the nature of the study requirements prior to enrollment and periodically throughout the study. The subject's well being will be continuously monitored by the experimenter, and the

Principal Investigator will report all serious adverse events in an expedited manner to the Duke University Health System (DUHS) Institutional Review Board (IRB) office and all applicable regulatory authorities in accordance with the Center's standard operating procedures.

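### The fMRI score meant to predict the rTMS effect is itself a pre/post stimulation change, so the regression tests association between two changes, not prediction from the pre-stimulation state

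*Combined protocol and SAP*

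**What the plan says.** Under Data Analysis & Statistical Considerations, the fMRI data paragraph builds one score per subject. First, "the imaging data from the pre and post fMRI sessions will be log transformed and subtracted from each other at each site in each subject". Those differences are centred within subjects and across subjects, and then: "This will be cross-correlated with the patterns previously found in order to quantify pattern expression for individual subjects in the present group". This is the pattern expression. The paragraph ends by saying that "pattern expression will be used to predict rTMS effects on writing task performance", with "differences in RT with active and sham rTMS" as the example outcome. No score from a single session is defined.

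The scan schedule is in Design & Procedures. Visit 2 is the baseline scan ("To assess patient's baseline, subjects will copy a sentence" in the scanner, alternating with rest). For Visits 3 to 5, step 4 says: "Subject will undergo fMRI after each of the 3 TMS visits". The same step places a writing task inside each stimulation block and a writing assessment immediately before and after it. The sample size paragraph names fMRI, together with the writing task, as an outcome measure in the TMS group of 20 patients.

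**The concern.** A predictor of treatment response should be fixed before treatment. Here the score contains a scan taken after stimulation, and the plan elsewhere treats fMRI as an outcome. One response is therefore regressed on another, and the result is called prediction.

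There is also a plain route to significance that involves no prediction. The baseline scan task is writing. If the post scans use the same task, as a pre/post subtraction implies, a patient whose writing changed may show a changed BOLD signal for that reason alone.

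The interpretation is what is at stake. In a study meant to develop a therapy, a significant result would be read as a network that identifies who benefits from rTMS. It could equally show only that brain activity and writing changed together. Conversely, a real baseline predictor could go undetected because no analysis looks for it.

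**Working it through.** The plan gives no sample size, alpha or power for this regression, so there is no figure to reproduce.

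**Inputs from the documents.** n = 20 focal hand dystonia patients, the group assigned both active and sham visits. Alpha = 0.05, stated only for the writing power analysis.

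**Assumptions.** Two-sided test. Scan-rescan correlation r of 0.6 or 0.8. The post scan reflects the writing effect with coefficient b of 0.2 to 0.5 SD per SD. A single post scan enters the score. Subtraction is taken as post minus pre; the opposite direction changes only the sign.

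**Timing.** Visit 2 is the only scan before stimulation, and the other three each follow a TMS visit. Whichever pair is chosen, one member is a post-stimulation scan that follows that visit's writing data.

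**Model.** Baseline expression P and rTMS effect E have unit variance and correlation ρ. Post = r·P + √(1−r²)·noise + b·E. Change D = Post − P. Then

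corr(D, E) = [b − ρ(1−r)] / √[2(1−r) + b² − 2bρ(1−r)].

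At n = 20 the critical absolute correlation is 0.444. Rejection rates below come from 40,000 simulated trials per setting.

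**Case 1: baseline unrelated to the effect (ρ = 0).** The formula reduces to b/√[2(1−r) + b²]. For b = 0.2 and r = 0.6 this is 0.2/√0.84 = 0.22. For b = 0.5 and r = 0.8 it is 0.5/√0.65 = 0.62.

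| b | Change score, r = 0.6 | Change score, r = 0.8 | Baseline score |
|---|---|---|---|
| 0.2 | 15% | 25% | 5% |
| 0.3 | 28% | 49% | 5% |
| 0.4 | 44% | 71% | 5% |
| 0.5 | 62% | 87% | 5% |

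With b = 0 the change score also rejects 5% of the time, so it keeps its level for its own null.

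**Case 2: baseline truly correlated with the effect (ρ = 0.6).** The baseline score rejects in about 84% of trials. The change score gives (positive / negative rejections):

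| b | r = 0.6 | r = 0.8 |
|---|---|---|
| 0.2 | 1.7% / 4.0% | 8% / 0.7% |
| 0.3 | 4.8% / 1.3% | 22% / 0.1% |
| 0.4 | 12% / 0.3% | 45% / 0% |
| 0.5 | 24% / 0.1% | 69% / 0% |

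Totals run from about 6% (1.7 + 4.0 = 5.7) to 69%. With b = 0 the totals are 21% (r = 0.6) and 13% (r = 0.8), nearly all negative under this subtraction direction.

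**Check on the planned processing.** A separate simulation followed the plan's steps (log, subtract, centre twice, correlate with a fixed pattern), with 30 regions assumed, change independent of baseline, and 3,000 trials. With baseline unrelated to the effect and change-effect correlations of 0.2, 0.3, 0.5 and 0.7, the planned score rejected in 11.7%, 22.9%, 56.4% and 93.5% of trials. The baseline score stayed near 5%. With a baseline correlation of 0.5 and none for change, the baseline score rejected in 56% to 64% of trials, depending on how expression was computed, and the planned score in 5%.

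**The case against.** The best defence is that, in regression, to predict often means only to associate. The Background frames the fMRI hypothesis as improved striatal activity after TMS, which is target engagement. Relating change in network expression to the active-sham writing difference serves that aim. Nothing in the plan says that prediction is from baseline or that the trial seeks to identify responders. On this reading the test is sound and only its label is wrong. That largely stands. It does not remove the point, because the plan never states the associative meaning, and its own data-management rules require the statistical approach to be set in advance and clearly stated.

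Three stronger readings are tempting and are not supported.

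- A reader might infer an inflated type I error. The 15% to 87% rates are power to detect an association between changes that the simulation put in. They are not false positives for the test's own null.
- A reader might infer that a true baseline predictor would appear with the wrong sign. The plan says only that the sessions are subtracted from each other. Even with post minus pre, negative rejections dominate in just one of the eight Case 2 settings, at 4%, and otherwise only at b = 0.
- A reader might infer that the scan always follows the whole outcome. That is true within a visit. For an active-sham contrast across visits a week apart, the scan after the earlier visit precedes the later visit's writing, though it still follows half of the contrast.

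It is also fair that this is an additional analysis in a 20-patient pilot, with no decision attached to it.

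**Conclusion.** The concern holds as a mismatch between the stated question and the test. The planned score necessarily contains post-stimulation data, so the regression cannot show whether pre-stimulation network expression predicts the rTMS effect. It validly tests whether two changes are associated.

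That conclusion follows from the definition of the score and the scan schedule and needs no simulation. The size does rest on assumptions: the coefficient b, the scan-rescan correlation, the true baseline correlation of 0.6, and the use of a single post scan. Within those ranges, the planned regression would often be significant with no baseline prediction present. With such prediction present, it ranges from near its nominal level to 69% rejection, against about 84% for a baseline score. The sign of the change-score result depends on the same assumptions and on the unstated subtraction direction, so no claim about its direction is warranted.

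The point should be addressed because it alters what may be concluded, although the analysis is secondary.

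**What to change.** In the fMRI data paragraph:

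1. For the prediction analysis, compute pattern expression from the Visit 2 scan alone and regress each patient's active-minus-sham writing effect on it.
2. Keep the pre/post change-score regression as a separate analysis, labelled as an association between changes (a correlate of response), not as prediction.
3. For that second analysis, state the direction of subtraction and which post-TMS scan or scans enter the score.

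Adjusting for in-scanner writing is not proposed. Tablet recording in the scanner is described only for Visit 2, and the adjustment might remove the signal of interest.

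The cost is a few sentences and one extra score per patient from scans already planned, with no new data or visits. The one loss is that the change-change result can no longer be presented as prediction.
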